5.3.2 Serious Adverse Events (Immediately Reportable to the Sponsor)

An SAE is any AE that meets any of the following criteria:

- Is fatal (i.e., the AE actually causes or leads to death)
- Is life threatening (i.e., the AE, in the view of the investigator, places the patient at immediate risk of death)
- This does not include any AE that, had it occurred in a more severe form or was allowed to continue, might have caused death.
- Requires or prolongs inpatient hospitalization (see Section 5.4.5.11)
- Results in persistent or significant disability/incapacity (i.e., the AE results in substantial disruption of the patient's ability to conduct normal life functions)
- Is a congenital anomaly/birth defect in a neonate/infant born to a mother exposed to study drug
- Is a significant medical event in the investigator's judgment (e.g., may jeopardize the patient or may require medical/surgical intervention to prevent one of the outcomes listed above)

The terms "severe" and "serious" are not synonymous. Severity refers to the intensity of an AE (e.g., rated as mild, moderate, or severe, or according to NCI CTCAE; see Section 5.4.3); the event itself may be of relatively minor medical significance (such as severe headache without any further findings).

Severity and seriousness need to be independently assessed for each adverse event recorded on the eCRF.

Serious adverse events are required to be reported by the investigator to the Sponsor immediately (i.e., no more than 24 hours after learning of the event; see Section 5.5.2 for reporting instructions).

5.3.3 Adverse Events of Special Interest (Immediately Reportable to the Sponsor)

Adverse events of special interest are required to be reported by the investigator to the Sponsor immediately (i.e., no more than 24 hours after learning of the event; see Section 5.5.2 for reporting instructions). Adverse events of special interest for this study are as follows.

Adverse Events of Special Interest Related to Drug Development in General:

- Cases of potential drug-induced liver injury that include an elevated ALT or AST in combination with either an elevated bilirubin or clinical jaundice, as defined by Hy's Law (see Section 5.4.5.7)

- Suspected transmission of an infectious agent by the study drug, as defined below:
Any organism, virus, or infectious particle (e.g., prion protein transmitting transmissible spongiform encephalopathy), pathogenic or non-pathogenic, is considered an infectious agent. A transmission of an infectious agent may be suspected from clinical symptoms or laboratory findings that indicate an infection in a patient exposed to a medicinal product. This term applies only when a contamination of the study drug is suspected.

Adverse Events of Special Interest Relevant to PRM-151:

- Suspected IRR with NCI CTCAE Grade ≥ 2
- Suspected anaphylactic and hypersensitivity reactions (all grades)
- Acute or suspected exacerbation of IPF (all grades)

5.3.4 Collection of Survival Data (Cohort C)

All efforts will be made to collect survival data for patients in Cohort C. Survival data collection will be accomplished remotely (i.e., via telephone or electronically), provided these communications are well documented.

Information on survival may be collected in multiple ways, including telephone calls or patient medical records, approximately every 6 months until death, or study termination by the Sponsor.

Women who become pregnant during the WA42293 study or in Cohort A or B of the WA42294 study can join Cohort C of WA42294 study.

If a patient is lost to follow-up or withdraws consent from the study, survival status will be ascertained through the use of Death Registries, where approved and available.

5.3.5 Lung Transplantation

Qualification for lung transplant will be assessed by the investigator. In general, qualification for lung transplant may be regarded as the point in time when a patient would be referred for evaluation for lung transplantation using local guidelines or practice, under ideal circumstances (e.g., no obvious contraindication for lung transplant). When applicable, date of qualification as assessed by investigator will be collected. Date of actual lung transplantation will be collected, when applicable.

5.4 METHODS AND TIMING FOR CAPTURING AND ASSESSING SAFETY PARAMETERS

The investigator is responsible for ensuring that all adverse events (see Section 5.3.1 for definition) are recorded on the Adverse Event eCRF and reported to the Sponsor in accordance with instructions provided in this section and in Sections 5.5–5.7.

For each AE recorded on the Adverse Event eCRF, the investigator will make an assessment of seriousness (see Section 5.3.2 for seriousness criteria), severity (see Section 5.4.3), and causality (see Section 5.4.4).

5.4.1 Adverse Event Reporting Period

Investigators will seek information on adverse events at each patient contact. All AEs, whether reported by the patient or noted by study personnel, will be recorded in the patient's medical record and on the Adverse Event eCRF.

After informed consent has been obtained but prior to initiation of study drug, only SAEs caused by a protocol-mandated intervention (e.g., invasive procedures such as biopsies, discontinuation of medications) should be reported (see Section 5.5.2 for instructions for reporting serious adverse events). For patients in Cohort A and B, all other medical occurrences that begin before the start of study treatment but after obtaining informed consent will be recorded on the General Medical History and Baseline Conditions eCRF, and not on the Adverse Event eCRF. Adverse events that are ongoing from study WA42293 for Cohort B patients will be transferred over from the WA42293 database in the WA42294 Adverse Event eCRF.

After initiation of study drug, all AEs will be reported until 8 weeks after the final dose of study drug.

Instructions for reporting AEs that occur after the adverse event reporting period are provided in Section 5.7.

5.4.2 Eliciting Adverse Event Information

A consistent methodology of non-directive questioning should be adopted for eliciting adverse event information at all patient evaluation timepoints. Examples of non-directive questions include the following:

"How have you felt since your last clinic visit?"

"Have you had any new or changed health problems since you were last here?"

5.4.3 Assessment of Severity of Adverse Events

The adverse event severity grading scale for the NCI CTCAE (v5.0) will be used for assessing adverse event severity (see Appendix 9). Table 3 will be used for assessing severity for AEs that are not specifically listed in the NCI CTCAE.

Table 3 Adverse Event Severity Grading Scale for Events Not Specifically Listed in NCI CTCAE

Grade	Severity
1	Mild; asymptomatic or mild symptoms; clinical or diagnostic observations only; or intervention not indicated
2	Moderate; minimal, local, or non-invasive intervention indicated; or limiting age-appropriate instrumental activities of daily living ^a
3	Severe or medically significant, but not immediately life-threatening; hospitalization or prolongation of hospitalization indicated; disabling; or limiting self-care activities of daily living ^{b, c}
4	Life-threatening consequences or urgent intervention indicated ^d
5	Death related to adverse event ^d

NCI CTCAE=National Cancer Institute Common Terminology Criteria for Adverse Events.

Note: Based on the most recent version of NCI CTCAE (v5.0), which can be found at:

http://ctep.cancer.gov/protocolDevelopment/electronic_applications/ctc.htm

^a Instrumental activities of daily living refer to preparing meals, shopping for groceries or clothes, using the telephone, managing money, etc.

^b Examples of self-care activities of daily living include bathing, dressing and undressing, feeding oneself, using the toilet, and taking medications, as performed by patients who are not bedridden.

^c If an event is assessed as a "significant medical event," it must be reported as a serious adverse event (see Section 5.5.2 for reporting instructions), per the definition of serious adverse event in Section 5.3.2.

^d Grade 4 and 5 events must be reported as serious adverse events (see Section 5.5.2 for reporting instructions), per the definition of serious adverse event in Section 5.3.2.

5.4.4 Assessment of Causality of Adverse Events

Investigators should use their knowledge of the patient, the circumstances surrounding the event, and an evaluation of any potential alternative causes to determine whether an adverse event is considered to be related to the study drug, indicating "yes" or "no" accordingly. The following guidance should be taken into consideration:

- Temporal relationship of event onset to the initiation of study drug
- Course of the event, with special consideration of the effects of discontinuation of study drug, or reintroduction of study drug (as applicable)
- Known association of the event with the study drug or with similar treatments
- Known association of the event with the disease under study
- Presence of risk factors in the patient or use of concomitant medications known to increase the occurrence of the event
- Presence of non-treatment-related factors that are known to be associated with the occurrence of the event

5.4.5 Procedures for Recording Adverse Events

Investigators should use correct medical terminology/concepts when recording adverse events on the Adverse Event eCRF. Avoid colloquialisms and abbreviations.

Only one adverse event term should be recorded in the event field on the Adverse Event eCRF.

5.4.5.1 Infusion-Related Reactions

Adverse events that occur during or within 24 hours after study drug administration and are judged to be related to study drug infusion should be captured as a diagnosis (e.g., "infusion-related reaction", or "anaphylactic reaction") on the Adverse Event eCRF. If possible, avoid ambiguous terms such as "systemic reaction". Associated signs and symptoms should be recorded on the dedicated Infusion-Related Reaction eCRF. If a patient experiences both a local and systemic reaction to the same dose of study drug, each reaction should be recorded separately on the Adverse Event eCRF, with signs and symptoms also recorded separately on the dedicated Infusion-Related Reaction eCRF.

5.4.5.2 Diagnosis versus Signs and Symptoms

A diagnosis (if known) should be recorded on the Adverse Event eCRF rather than individual signs and symptoms (e.g., record only liver failure or hepatitis rather than jaundice, asterixis, and elevated transaminases). However, if a constellation of signs and/or symptoms cannot be medically characterized as a single diagnosis or syndrome at the time of reporting, each individual event should be recorded on the Adverse Event eCRF. If a diagnosis is subsequently established, all previously reported adverse events based on signs and symptoms should be nullified and replaced by one adverse event report based on the single diagnosis, with a starting date that corresponds to the starting date of the first symptom of the eventual diagnosis.

5.4.5.3 Adverse Events That Are Secondary to Other Events

In general, adverse events that are secondary to other events (e.g., cascade events or clinical sequelae) should be identified by their primary cause, with the exception of severe or serious secondary events. A medically significant secondary adverse event that is separated in time from the initiating event should be recorded as an independent event on the Adverse Event eCRF. For example:

- If vomiting results in mild dehydration with no additional treatment in a healthy adult, only vomiting should be reported on the eCRF.
- If vomiting results in severe dehydration, both events should be reported separately on the eCRF.
- If a severe gastrointestinal hemorrhage leads to renal failure, both events should be reported separately on the eCRF.
- If dizziness leads to a fall and consequent fracture, all three events should be reported separately on the eCRF.

- If neutropenia is accompanied by an infection, both events should be reported separately on the eCRF.

All adverse events should be recorded separately on the Adverse Event eCRF if it is unclear as to whether the events are associated.

5.4.5.4 Persistent or Recurrent Adverse Events

A persistent adverse event is one that extends continuously, without resolution, between patient evaluation timepoints. Such events should only be recorded once on the Adverse Event eCRF. The initial severity (intensity or grade) of the event will be recorded at the time the event is first reported. If a persistent adverse event becomes more severe, the most extreme severity should also be recorded on the Adverse Event eCRF. If the event becomes serious, it should be reported to the Sponsor immediately (i.e., no more than 24 hours after learning that the event became serious; see Section 5.5.2 for reporting instructions). The Adverse Event eCRF should be updated by changing the event from "non-serious" to "serious," providing the date that the event became serious, and completing all data fields related to serious adverse events.

A recurrent adverse event is one that resolves between patient evaluation timepoints and subsequently recurs. Each recurrence of an adverse event should be recorded as a separate event on the Adverse Event eCRF.

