5.4.5.9 Preexisting Medical Conditions

A preexisting medical condition is one that is present prior the first dosing visit for this study. Such conditions should be recorded on the General Medical History and Baseline Conditions eCRF.

A preexisting medical condition should be recorded as an adverse event only if the frequency, severity, or character of the condition worsens during the study. When recording such events on the Adverse Event eCRF, it is important to convey the concept that the preexisting condition has changed by including applicable descriptors (e.g., "more frequent headaches").

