6.3.1 Adverse Events

Verbatim descriptions of TEAE will be coded using the most current version of the Medical Dictionary for Regulatory Activities (MedDRA) and adverse event severity will be graded according to NCI CTCAE v5.0 scale. A TEAE is defined as any new adverse event reported or any worsening of an existing condition on or after the first dose of study drug.

The incidence and observation time-adjusted rate will be summarized, as appropriate. In addition, separate summaries will be generated for serious adverse events, deaths, adverse events of special interest, and adverse events leading to discontinuation of PRM-151. Adverse events will be summarized by mapped term, appropriate thesaurus level, and toxicity grade.

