5.3.2 Adverse Events

All verbatim (“investigator-reported”) AE terms will be assigned a standardized term (the “Preferred Term [PT]”) and a superclass term using the most current version of the Medical Dictionary for Regulatory Activities (MedDRA) thesaurus terms, and adverse event severity will be graded according to NCI CTCAE v5.0 scale. A by-patient AE data listing including onset study day, duration, PT, treatment, severity, relationship to treatment, treatment for AE, action taken, and outcome will be provided.

All AEs, SAEs, AEs leading to death, AESIs, and AEs leading to study treatment discontinuation that occur during or after the first dose of study treatment (i.e., treatment emergent adverse events [TEAEs]) will be summarized by PT and severity grade as appropriate. An exacerbation or worsening of a pre-existing condition will be considered treatment-emergent only if the most extreme intensity is greater than the intensity at baseline (i.e., the intensity for a given AE increases and its end date is on or after the date of the first dose in the OLE study). For events of varying severity, the highest grade will be used in the summaries. Listings of AEs, SAEs, and AESIs will also be produced. Any non-treatment emergent SAEs, will also be listed separately (SAE occurring in Cohorts A, B, and C before or after the AE reporting period, as described in Protocol Section 5.4 and Protocol Section 5.7).

Number of patients with AE, number of AEs, cumulative incidence of AE as well as the AE rate per 100 patient-years exposure (defined as the number of events/total duration in the study multiplied by 100) will be calculated, along with the corresponding 95% confidence intervals (CIs) for the patient-years' rates of the SOC (exact based on the Chi-square distribution [Ulm 1990]).

Summary tables of the following will be provided for each cohort and the treatment groups as described in Section 5.1.1, including, but not limited to:

- AEs and SAEs of any grade
- AEs by highest NCI CTCAE grade
- Severe AEs (NCI CTCAE Grade 3 or above)
- AEs leading to death
- AEs leading to study treatment discontinuation
- AEs leading to drug interruption
- AEs leading to withdrawal from study
- Treatment related AEs and SAEs
- AESIs defined as follows:

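### A WA42293 adverse event carried into the extension that becomes serious there at an unchanged grade is left out of the SAP's treatment-emergent AE and SAE tables

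*Protocol*

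**What the plan says.** **Definition.** Protocol Section 6.3.1 treats as treatment-emergent any new adverse event and "any worsening of an existing condition on or after the first dose of study drug". SAP Section 5.3.2 is narrower: a worsened pre-existing condition "will be considered treatment-emergent only if the most extreme intensity is greater than the intensity at baseline". The SAP explains this as meaning that "the intensity for a given AE increases and its end date is on or after the date of the first dose" in the extension. The SAP introduction says the SAP supersedes the protocol's analysis plan. Its Appendix 1, on changes to protocol-planned analyses, lists only the healthcare-utilization objective.

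**Recording.** Under Protocol Section 5.4.1, events ongoing from the parent study in Cohort B "will be transferred over from the WA42293 database in the WA42294 Adverse Event eCRF". Under Section 5.4.5.4 a persistent event has one record ("Such events should only be recorded once on the Adverse Event eCRF"). If it becomes serious, that record is changed from non-serious to serious, "providing the date that the event became serious". Section 5.3.2 adds: "Severity and seriousness need to be independently assessed for each adverse event recorded on the eCRF". Under Section 5.4.5.9 a pre-existing condition is "recorded as an adverse event only if the frequency, severity, or character of the condition worsens during the study".

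**Outputs.** SAP Section 5.3.2 describes its summaries of AEs, SAEs, fatal AEs, AESIs and AEs leading to treatment discontinuation as summaries of treatment-emergent events. It also promises general AE, SAE and AESI listings. A separate listing of non-treatment-emergent SAEs is described as covering SAEs before or after the AE reporting period.

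**The concern.** The protocol keeps seriousness and severity apart, so an event can become serious without changing grade. The SAP's test looks only at grade. For an event that starts in the extension this does not matter, because its onset date makes it treatment-emergent. For an event already open at the first extension dose, the grade test is the only way into the tables.

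Long-term safety is the first-listed objective, and the incidence of AEs and the proportion stopping treatment because of AEs are named safety endpoints. A rule that drops some events that became serious on open-label drug can only make those summaries look better. It also departs from the protocol without saying so.

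**Working it through.** No arithmetic applies: neither document gives a figure for this, and neither gives a count of parent-study events ongoing at entry. The check is to take each kind of change in an event already open at the first extension dose and follow it through the recording rules and both definitions.

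| Change in the extension | Record on the AE form | Protocol 6.3.1 | SAP 5.3.2 |
|---|---|---|---|
| 1. Grade rises | Same record, higher worst grade | Counted | Counted |
| 2. Becomes serious, grade unchanged | Same record, edited to serious and dated | Counted, if becoming serious is a worsening | Not counted |
| 3. Grade 1–2 event (not listed in CTCAE) comes to need hospitalization | Same record; Protocol Table 3 makes it Grade 3 | Counted | Counted, because the grade rises |
| 4. Resolves, then recurs | New record with onset in the extension (5.4.5.4) | Counted | Counted as a new event |
| 5. Pre-existing condition entered on the AE form as worse in frequency or character (5.4.5.9) | First AE entry is made during the extension | Counted | Unclear |

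Case 2 is the gap. It can occur in practice. Table 3 places events that are disabling, that limit self-care, or for which hospitalization is indicated all in Grade 3, so a non-serious Grade 3 event that later leads to admission can stay Grade 3. Nor is admission required: Protocol Section 5.3.2 also makes an event serious if the investigator judges it medically significant.

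Case 5 turns on which SAP sentence governs. One admits events that occur during or after the first dose, and an entry first made in the extension could qualify. The other requires a rise in intensity for any worsening of a pre-existing condition. The SAP does not say which takes precedence.

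For case 2, the outputs are affected as follows:

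- **AE and SAE summary tables:** absent.
- **Rates per 100 patient-years:** absent, on the natural reading that they use the same events as the tables.
- **Summary of AEs leading to treatment discontinuation:** absent if the event leads to stopping drug. SAP Section 5.2 still summarizes reasons for discontinuation.
- **General AE and SAE listings:** should be present.
- **Separate listing of non-treatment-emergent SAEs:** may be absent. An event that became serious inside the reporting period fits neither half of the listing's description, although its earlier onset might lead a programmer to include it.

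**The case against.** The best case against is that the gap is narrow and that much of what it might hide is reported elsewhere. Most of that stands.

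- Recurrences are new records, and many events that turn serious through hospitalization also rise in grade. Protocol Section 5.4.5.3 excepts severe or serious secondary events from being folded into their primary cause, so a serious complication can bring its own record.
- A reader might infer that every worsening in frequency or character is lost. The documents do not support that: recurrences are counted, and for conditions re-entered under Section 5.4.5.9 the SAP is ambiguous rather than exclusionary. Its explanation of the grade test fits best an AE record already open at Day 1.
- A reader might infer that acute exacerbations drop out because IPF pre-exists in every patient. That is strained. An acute exacerbation is a discrete event with its own diagnostic criteria. SAP Section 5.5 tabulates the number, yearly rate and patients affected, and Section 5.5.1 analyses time to first event; neither section invokes the treatment-emergent rule.
- A reader might infer that the affected events survive only in listings. Respiratory hospitalizations are analysed in SAP Sections 5.5 and 5.5.1, discontinuation reasons in 5.2, and deaths and their causes in 5.3.2. A fatal event graded 5 under Table 3 also passes the grade test.
- Safety surveillance is not weakened: Protocol Section 5.4.5.4 requires reporting within 24 hours of learning that an event became serious.

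What these points do not answer is case 2 itself. The alternative hospitalization outputs are respiratory only, and no listing contributes to an incidence table or a rate.

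**Conclusion.** The point holds in a limited form. SAP Section 5.3.2 narrows the protocol's definition without declaring it. Combined with the carry-over and single-record rules, this leaves a Cohort B event that becomes serious in the extension at an unchanged grade out of the treatment-emergent AE and SAE tables and the patient-year rates. Where such an event leads to stopping drug, it is also left out of the summary of AEs leading to discontinuation.

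The direction is certain, since exclusion can only lower counts. The size is not. Any percentage would need the share of AE records already open at entry and the share of those that turn serious without a grade change; the documents give neither, and the number may be small. The conclusion assumes that becoming serious counts as a worsening under Protocol Section 6.3.1, and that the patient-year rates use the same events as the tables. It does not extend to a general loss of exacerbations, respiratory hospitalizations, deaths or recurrent events.

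**What to change.** 1. In SAP Section 5.3.2, add that a pre-existing or carried-over event is treatment-emergent, and is a treatment-emergent SAE, if its became-serious date is on or after the first extension dose. Protocol Section 5.4.5.4 already requires that date on the AE form.
2. For other kinds of worsening, either align the wording with Protocol Sections 6.3.1 and 5.4.5.9, stating how same-grade changes in frequency or character are tabulated, or declare the narrower definition in Appendix 1. The protocol shows only free-text descriptors for such changes, so tabulating them may need a coding rule.
3. Extend the listing of non-treatment-emergent SAEs to any SAE active during the extension's reporting period that is not in the tables.

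The cost is a short SAP amendment, minor programming and slightly higher AE and SAE counts. Item 1 needs no new data collection.
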